14.1	DATA COLLECTION AND MANAGEMENT RESPONSIBILITIES.....	31
14.2	STUDY RECORDS RETENTION.....	31
14.3	PROTOCOL DEVIATIONS	32
14.4	PUBLICATION AND DATA SHARING POLICY.....	32
15	STUDY FINANCES	33
15.1	FUNDING SOURCE.....	33
15.2	COSTS TO THE PARTICIPANT.....	33
16	STUDY ADMINISTRATION	33
16.1	STUDY LEADERSHIP	33
17	CONFLICT OF INTEREST POLICY	33
18	REFERENCES	34
19	ATTACHMENTS	36
20	SCHEDULE OF EVENTS	41

CONFIDENTIAL

This material is the property of the NYU School of Medicine and Langone Medical Center. Do not disclose or use except as
authorized in writing by the study sponsor
Interventional Template Version: 11 January 2019

List of Abbreviations

AE	Adverse Event/Adverse Experience
SAE	Serious Adverse Event
GSM	Genitourinary syndrome of menopause
HLA	Hyaluronic acid
VSQ	Vulvovaginal symptom questionnaire
VSI	Vaginal Symptom Index
FSFI	Female Sexual Function Index
VMI	Vaginal maturation index
MCG	Micrograms
ASCCP	American Society of Colposcopy and Cervical Pathology
VAS	Visual analog scale
PGI-I	Patient global impression of improvement
HIPAA	Health Insurance Portability and Accountability Act
IRB	Institutional Review Board
N	Number (typically refers to participants)
NIH	National Institutes of Health
OHRP	Office for Human Research Protections
OHSR	Office of Human Subjects Research
PI	Principal Investigator
QA	Quality Assurance
QC	Quality Control
US	United States

CONFIDENTIAL

This material is the property of the NYU School of Medicine and Langone Medical Center. Do not disclose or use except as authorized in writing by the study sponsor
Interventional Template Version: 11 January 2019

Protocol Summary

Title	A randomized, single center study comparing hyaluronic acid to vaginal estrogen for treatment of genitourinary syndrome of menopause
Short Title	HLA vs vaginal estrogen for treatment of GSM
Brief Summary	Non-hormonal alternatives for the treatment of genitourinary syndrome of menopause (GSM) are needed. In this proposed trial, patients who are diagnosed with GSM will be randomized to receive either a hyaluronic acid (HLA) vaginal insert or vaginal estrogen topical cream for 12 weeks. There will be a baseline visit and a 12 week follow up visit, at which points the patient will undergo a detailed history and physical examination including a pelvic exam, vaginal pH sampling, vaginal cell sample for microscopic analysis, and will fill out questionnaires (vulvovaginal symptom questionnaire (VSQ), vaginal symptom index (VSI), and female sexual function index (FSFI)). These study arms will be analyzed to assess the efficacy of HLA as compared to the gold standard of vaginal estrogen to treat GSM symptoms.
Phase	Pilot
Objectives	The primary objective is to assess the feasibility and acceptability of the proposed intervention of HLA insert as measured by the vulvovaginal system questionnaire (VSQ). Secondary objectives include the assessment of preliminary effectiveness of the HLA insert to improve GSM symptoms and GSM physical exam measures, as compared to vaginal estrogen.
Methodology	This is an open label, randomized, active control, parallel group study.
Endpoint	The primary endpoint is the VSQ – 21 item questionnaire that measures patient quality of life via GSM symptoms, their emotional impact, sexual impact, and life impact. Secondary endpoints include study treatment compliance and retention through 12 weeks, vaginal maturation index (VMI), vaginal pH, vaginal rugal folds, and subjective changes in the visual analog scale (VAS) scores for dyspareunia, vaginal itching, and dryness in participants receiving HLA insert as compared to those receiving vaginal estrogen.
Study Duration	1 year
Participant Duration	12 weeks
Duration of IP administration	12 weeks
Population	Post-menopausal women in New York

CONFIDENTIAL

This material is the property of the NYU School of Medicine and Langone Medical Center. Do not disclose or use except as authorized in writing by the study sponsor

[figure not shown]
Interventional Template Version: 11 JAN 2019

Study Sites	[name]
Number of participants	40
Description of Study Agent/Procedure	HLA Vaginal insert: 5mg of active medication in 2g vaginal insert
Reference Therapy	Vaginal estrogen cream, estradiol: 100mcg
Key Procedures	Sampling of vaginal tissue, sampling of vaginal pH
Statistical Analysis	Primary and secondary outcome measures will be summarized and described overall and by treatment group. Analysis will focus on the quality of life as well as objective measures of vaginal health improvement obtained in the HLA group, rather than hypothesis testing to compare outcomes to those receiving estrogen. Overall, and by treatment group, compliance and retention will be similarly described.

CONFIDENTIAL

This material is the property of the NYU School of Medicine and Langone Medical Center. Do not disclose or use except as authorized in writing by the study sponsor
Interventional Template Version: 11 January 2019

Schematic of Study Design

CONFIDENTIAL

This material is the property of the NYU School of Medicine and Langone Medical Center. Do not disclose or use except as authorized in writing by the study sponsor
Interventional Template Version: 11 January 2019

1 Key Roles

[name], principal investigator
Gynecology
[name]
[contact]
[contact]

[name], site investigator
Female Pelvic Medicine and Reconstructive Surgery
[name]
[contact]
[contact]

[name], site investigator
Female Pelvic Medicine and Reconstructive Surgery
[name]
[contact]
[contact]

[name], site investigator
Female Pelvic Medicine and Reconstructive Surgery
[name]
[contact]
[contact]

[name], site investigator
Obstetrics & Gynecology
[name]
[contact]
[contact]

[name], collaborator
Female Pelvic Medicine and Reconstructive Surgery
University of Pennsylvania, Philadelphia, PA
[contact] [contact]

[name], site investigator
Obstetrics & Gynecology
[name]
[contact]
[contact]

[name], site investigator
Female Pelvic Medicine and Reconstructive Surgery
[name]
[contact]

CONFIDENTIAL

This material is the property of the NYU School of Medicine and Langone Medical Center. Do not disclose or use except as authorized in writing by the study sponsor
Interventional Template Version: 11 January 2019

[contact]

[name], statistician
Biostatistics, Department of Population Health
[name]
[contact]
[contact]

[name], MS, statistician
Biostatistics, Department of Population Health
[name]
[contact]
[contact]

JDS Therapeutics, sponsor
[name]
[contact]

2 Introduction, Background Information and Scientific Rationale

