4.2 Study Endpoints

4.2.1 Primary Study Endpoints

The primary endpoint will be the change in the VSQ score, between the baseline visit and 12 week follow-up.

The VSQ is a 21-question survey developed in 2012 that specifically asks about GSM symptoms, their emotional impact, sexual impact, and life impact. Among 120 post-menopausal women, this questionnaire was found to have reliability and internal consistency (15). Most importantly, in the absence of a gold standard instrument to assess the quality of life impact of

CONFIDENTIAL

This material is the property of the NYU School of Medicine and Langone Medical Center. Do not disclose or use except as authorized in writing by the study sponsor
Interventional Template Version: 11 January 2019

GSM, this questionnaire is critical. It is more nuanced and disease-specific than VAS scoring, and thus far, an underutilized tool to understand the significant psychological impact of this disease. Because GSM is a symptom-driven disease and patients will likely adhere to a treatment plan if they perceive symptomatic improvement, this study's primary endpoint of treatment success will be measured by improvement in VSQ scoring.

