10.1 Statistical and Analytical Plans (SAP)

As the study is a pilot randomized trial, the results are expected to inform the overall protocol design for a larger effectiveness evaluation, including the statistical analysis plan. Our overall strategy will be to estimate the primary and secondary outcomes for those randomized to HLA, along with the contemporary cohort randomized to vaginal estrogen. Formal comparisons between randomized groups are not of focus, but we will estimate treatment effects along with measures of variability in these measures (95% CI).

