10.2 Statistical Hypotheses

We expect no clinically meaningful differences in baseline characteristics or baseline assessment of outcomes between those randomized to HLA or to vaginal estrogen, however this is possible given the limited pilot trial sample size. These differences will be assessed and considered in the evaluation of outcomes for primary and secondary endpoints.

We expect a clinically meaningful improvement in the change measured at 12 weeks (comparison of VSQ at 12 weeks, adjusted for baseline) in VSQ in the HLA group, and expect this to be greater as compared to those randomized to vaginal estrogen. Similarly, we expect to observe clinically meaningful improvements in the HLA group at 12 weeks, beyond those observed in those randomized to the vaginal estrogen cohort. These include VSI, FSFI, VAS for dyspareunia, itching, and dryness, vaginal pH, and presence of rugal folds.

CONFIDENTIAL

This material is the property of the NYU School of Medicine and Langone Medical Center. Do not disclose or use except as authorized in writing by the study sponsor
Interventional Template Version: 11 January 2019

These estimates will provide estimates for establishing effectiveness in future trials.

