10.4 Description of Statistical Methods

Baseline (pre-randomization) participant demographics and clinical characteristics will be summarized through descriptive statistics overall, and by randomized group. Clinical characteristics will include past HRT use, uterus present or not, and components of their medical and gynecologic history. Details of each outcome measure is provided below. Analysis of the primary and secondary measures will include summarizing each by the mean and standard deviation at baseline and all measured time points, including at the primary outcome time of 12 weeks. For continuous measures, a linear mixed effects regression model will estimate the mean outcome at 12 weeks, both unadjusted and adjusted for baseline measurement. No further adjustment for participant characteristics is expected given the limited trial size. The linear mixed effects regression model will allow all participants to be included in analysis, regardless of completion of study follow up at 12 weeks, under the assumption of this assessment being missing at random.

Missing outcome data will be summarized by participant characteristics to understand how to better retain individuals in treatment.

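### The plan centres on improvement within the HLA arm and formally names no single randomised VSQ difference as its effectiveness estimate

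*Combined protocol and SAP*

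**What the plan says.** - **Focus.** The Statistical Analysis row of the Protocol Summary describes outcomes overall and by group, but centres the analysis on improvement "obtained in the HLA group, rather than hypothesis testing to compare outcomes to those receiving estrogen".
- **Endpoint.** Section 4.2.1: "The primary endpoint will be the change in the VSQ score, between the baseline visit and 12 week follow-up". It adds that the "primary endpoint of treatment success will be measured by improvement in VSQ scoring"; section 2.1 says the same. Neither gives a threshold, an arm or a comparator.
- **Between-arm effect.** Section 10.1: "Formal comparisons between randomized groups are not of focus, but we will estimate treatment effects along with measures of variability", with 95% CIs. It does not say which effect.
- **Model.** Section 10.4: "a linear mixed effects regression model will estimate the mean outcome at 12 weeks, both unadjusted and adjusted for baseline measurement". Neither is labelled primary. The section expects no adjustment for other participant characteristics.
- **Direction of intent.** Section 10.2 describes the VSQ result in parentheses as a "comparison of VSQ at 12 weeks, adjusted for baseline". On baseline imbalance it says: "These differences will be assessed and considered in the evaluation of outcomes for primary and secondary endpoints".
- **Analysis sets.** Section 10.3 lists intent-to-treat and per-protocol sets, neither named primary.
- **Precision.** Section 10.5 expects, with at least 80% probability, a 95% CI width of 1.7 with 30 randomised per arm and SD 2. Sections 5.6 and 10.5 expect 40 evaluable out of 60.

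**The concern.** Randomisation exists so that changes unrelated to the product cancel between arms. A before-after change in one arm keeps them. Women enter because they have symptoms (5.1), the VSQ asks about the past week (attachment 19a), treatment is open label, and there is no placebo arm. Section 10.6.1 itself concedes possible bias in patient-reported improvement. A product with no effect could therefore show an improvement whose CI excludes zero.

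The second issue is choice. If unadjusted and adjusted results are both produced and neither is primary, the one to emphasise can be chosen after the data are seen. The estimates are meant to plan a larger effectiveness trial (10.2, 10.5), and the product's manufacturer funds the study (6.1.2, 15.1). A planning estimate should be one quantity, defined beforehand.

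**Working it through.** **1. The plan's own precision figure.** Inputs from 10.5: n = 30 per arm, SD 2, width 1.7, probability at least 80%. The SD is attached to an undefined label (VLM), taken here as the VSQ.

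For one arm's mean, the 80%-assured width is 2·t(0.975, n−1)·SD/√n · √[χ²(0.80, n−1)/(n−1)].

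- n = 30: 2 × 2.045 × 2/√30 = 1.49; × √(35.14/29) = 1.64.
- The probability that the width is at most 1.7 is P(χ² on 29 df ≤ 37.57) = 0.87. The plan's statement reproduces.

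For the difference between arms, replace SD/√n by SD·√(2/n) and use 2n−2 df.

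- 30 per arm: 2 × 2.002 × 2 × √(2/30) = 2.07; × √(66.82/58) = 2.22. The probability of a width at most 1.7 is 0.03.
- 20 per arm: 2 × 2.024 × 2 × √(2/20) = 2.56; × √(45.08/38) = 2.79.
- A width of 1.7 with 80% assurance would need 49 evaluable per arm.

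The stated precision is thus that of a single arm's mean, not of the randomised difference.

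**2. Within-arm change with no product effect.** Assumptions, none in the documents: mean entry score z SD above the long-run mean, and correlation r between baseline and week 12. The expected fall is z(1−r) SD and the SD of change is √[2(1−r)] SD. The t statistic is then noncentral with parameter z·√[n(1−r)/2]. Example: z = 1, r = 0.5, n = 20 gives √5 = 2.236 against a critical value of 2.093, so the CI excludes zero in 56% of trials.

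| Entry shift | r | n = 20 | n = 30 |
|---|---|---|---|
| 1 SD | 0.5 | 56% | 75% |
| 1 SD | 0.8 | 27% | 39% |
| 0.5 SD | 0.5 | 19% | 26% |
| 0.5 SD | 0.8 | 10% | 13% |

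The n = 20 column matches the 40 evaluable participants the plan expects.

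**3. Unadjusted against adjusted difference, true difference zero.** With equal SDs, the adjusted difference is the unadjusted one minus the slope times the chance baseline difference. At 20 per arm and r = 0.5:

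- SD of the gap: r·√(2/n) = 0.5 × √0.1 = 0.158 SD. Mean absolute gap: 0.158 × √(2/π) = 0.13 SD, or about 0.25 points at SD 2.
- Opposite signs: the two estimates correlate at √(1−r²), so the probability is arcsin(r)/π = 1/6, or 17%. For r = 0.3 and 0.7 it is about 10% and 25%.
- Bias from taking the better of the two: half the mean gap, 0.06 SD.

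Simulation with an estimated slope gives the same 17%, 0.13 SD and 0.06 SD.

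**4. Gain from adjustment.** The variance falls by up to r²: 25% at r = 0.5 and 49% at r = 0.7. Estimating the slope multiplies the remaining variance by 1 + 1/(2n−4) = 1 + 1/36. The realised cuts are therefore 1 − 0.75 × 1.028 = 23% and 1 − 0.51 × 1.028 = 48%.

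**The case against.** The plan is better than a quick reading suggests, and several stronger inferences fail.

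- *A reader might infer that success is defined as the HLA arm's own change.* No sentence says so. That reading joins the Summary's focus to the comparator-free wording of 4.2.1. The Objectives row of the Summary and section 3.1 are comparative, and 10.1 promises treatment effects with CIs.
- *A reader might count change from baseline as a third competing estimate.* Section 4.2.1 names the variable and 10.2 says how it is compared. With baseline as a covariate, analysing change or week-12 score gives the same treatment coefficient. No analysis section plans a raw between-arm comparison of change scores.
- *A reader might take the clause on considering baseline differences as free choice of covariates.* Section 10.4 expects no further adjustment, which limits that freedom.
- *A reader might speak of a false-positive rate.* This is a pilot without test, threshold or go/no-go rule, so the risk lies in interpretation. Entry requires symptoms but no minimum VSQ, so the size of any entry shift is unknown.

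It can also be said that comparison with an active control, without placebo or margin, cannot show that HLA works. That stands. The difference removes shifts common to both arms, but not expectation that differs between two openly given products.

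What remains is that the comparison is called not of focus, 10.4 lists two versions with equal standing, and the only pointer to the adjusted one is a parenthesis in the hypotheses section.

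**Conclusion.** The concern holds in a limited form. The documents support three facts: the stated focus is improvement in the HLA group, success is tied to VSQ improvement with no comparator, and no between-arm estimate is formally primary although 10.2 points to the baseline-adjusted one.

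Under the stated assumptions, an inert product would give a within-arm CI excluding zero in about 10-56% of trials at 20 evaluable per arm, or 13-75% at 30. That range rests wholly on the assumed entry shift and correlation and shows only how little a within-arm improvement proves. The freedom between unadjusted and adjusted differences is real but modest: 17% sign disagreement, a 0.13 SD mean gap and 0.06 SD selection bias at 20 per arm and correlation 0.5. The correction should be made because it is cheap and adds precision, not because the trial would otherwise be invalid.

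**What to change.** - **Summary, 4.2.1, 10.1 and 10.4:** name the intent-to-treat, baseline-adjusted week-12 VSQ difference (HLA minus estrogen) with 95% CI as the single primary effectiveness estimate. No test is needed.
- **Same places:** label unadjusted week-12 results and within-arm change as descriptive, and do not call within-arm improvement treatment success.
- **10.2:** state that baseline VSQ differences are handled by this pre-specified adjustment.
- **10.5:** say that the width of 1.7 applies to one arm's mean, and give the width for the difference: unadjusted and 80%-assured, about 2.2 at 30 per arm and 2.8 at 20 per arm. Define the label attached to the SD.

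The cost is wording in these sections; no new data, visits or analyses are needed. The downsides should be stated openly. The published precision becomes less favourable. The difference describes HLA relative to estrogen and does not by itself show that HLA works, and differential open-label expectation remains.

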2.1 Background Information and Relevant Literature

Genitourinary syndrome of menopause (also referred to as vulvovaginal atrophy, urogenital atrophy, and atrophic vaginitis) is a collection of vulvovaginal and urinary signs and symptoms that result from a decrease in estrogen (1). The most common symptoms include dryness, burning, dyspareunia, and urinary incontinence in menopausal women (2). The impact of these symptoms is widespread with 85% of women over the age of 40 who endorse vaginal dryness (3). Further, over half of the women with symptoms report that their quality of life is negatively impacted (4). Due to the deeply impactful effects of GSM, it is worthwhile to assess the mainstays of treatment and examine novel therapies in order to positively improve the quality of life of these women.

For many years, topical estrogen therapy has been the standard of care for GSM, after over-the-counter vaginal moisturizers and lubricants have failed (5). In many ways, estrogen is a logical treatment choice due to the fact that it replaces what is lost in post-menopausal women. The topical estrogen functions to maintain the collagen content in the epithelium, optimize genital blood flow, and maintain levels of acid mucopolysaccharides and hyaluronic acid (HLA) within the epithelium.

However, some patients may be uncomfortable with hormonal therapies or in certain circumstances hormonal therapies may be contraindicated, even in topical form. Therefore, it is important to explore non-hormonal alternatives for the treatment of this common condition.

One such novel therapy is topical HLA. HLA is a large non-sulfated glycosaminoglycan that forms in the plasma membrane of cells and serves three major functions (6). First, it helps maintain the extracellular matrix. Second, it contributes to cell proliferation and turn over. Third,

CONFIDENTIAL

This material is the property of the NYU School of Medicine and Langone Medical Center. Do not disclose or use except as authorized in writing by the study sponsor
Interventional Template Version: 11 January 2019

it modulates moisture in the epithelium. Currently, HLA is FDA approved for use in osteoarthritis (albeit with limited efficacy), and is used in the treatment of dry skin, dry eye, and youth-promoting cosmetic products. Recently, the potential role for HLA in the treatment of GSM has been uncovered.

In a study of rats randomly assigned to oophorectomy plus placebo, oophorectomy plus vaginal HLA gel, or sham oophorectomy, it was found that HLA resulted in a reversal of vaginal atrophy with no associated increase in uterine weight (7). This study is particularly promising because it not only shows the reversal of atrophy, but also it suggests that HLA has no effect on uterine weight (a proxy for endometrial lining) which is a feared complication of unopposed systemic estrogen therapy.

One of the earliest human studies examining the potential application of HLA for GSM symptoms as a non-hormonal alternative comes from Italy in 2006 (8). A pilot study of just 10 patients was initially performed to assess the safety profile of use of HLA gel on the vulva for GSM symptoms for 30 days. No side effects or adverse events were noted between the start and end of the usage period. No lab abnormalities were found aside from a ‘slight increase’ in monocyte percentage (9 to 13%) between the start and end, which the investigators deemed to be unrelated to the HLA treatment. Subsequently, a larger trial of 100 post-menopausal women was conducted by the same group of investigators. In this cohort, HLA was applied vaginally and studied over a period of 12 weeks. Using the visual analog scale (VAS) for GSM symptoms—specifically vaginal dryness, itching, burning, and dyspareunia—clinically significant improvement was noted from baseline to the end of the study period. Again, no adverse events or side-effects were noted for the gel usage.

In a similar study from Italy, an open trial of 150 post-menopausal women were given a vaginal insert that contained HLA, vitamin E, and vitamin A to use for four weeks (9). Subjective and objective vaginal markers were compared over the four weeks and significant improvement was observed in the primary endpoint of vaginal dryness as compared to baseline with no side-effects to the HLA insert reported.

An open RCT conducted in China in 2013 comparing vaginal HLA gel to vaginal estriol cream confirmed HLA’s overall efficacy and safety profile (10). Only mild adverse events were noted relating to HLA gel use. On laboratory testing, two patients were found to have vulvovaginal candidiasis and one patient was found to have bacterial vaginosis. These three patients had no symptoms, required no intervention, and the infections self-resolved. Only one patient was found to have symptomatic vulvovaginal candidiasis and was treated with no subsequent complications.

A small, recent study in Iran also noted the non-inferiority of vaginal HLA as compared to vaginal estrogen cream for symptomatic GSM (11). The study found that both treatment groups improved compared to baseline in dryness, itch, maturation index, pH, and a composite score of vaginal symptoms. However, only the HLA group showed improvement in symptoms of urinary incontinence. Further, improvement in the HLA group was significantly greater than the estrogen group for dryness, maturation index, and composite score. Meanwhile, a Turkish study found the opposite—vaginal estradiol tablets were more effective on improving vaginal symptoms as

CONFIDENTIAL

This material is the property of the NYU School of Medicine and Langone Medical Center. Do not disclose or use except as authorized in writing by the study sponsor
Interventional Template Version: 11 January 2019

compared to vaginal HLA tablets, but both treatments still significantly improved all vaginal symptoms studied (12).

Most studies above examined the individual parameters that make up the composite ‘vaginal health index score’ (13). The vaginal health index score is a tool that evaluates five parameters to establish the degree of vaginal atrophy: vaginal elasticity, vaginal secretions, pH, epithelial mucous membrane, and vaginal hydration. In congruence with the above studies, vaginal HLA use led to significant vaginal health index score improvements over time. In sum, the results of these international studies are promising in that they suggest a potential role for HLA use in the treatment of GSM as a non-hormonal alternative.

This study proposes comparing a HLA vaginal insert available in the US, Revaree, to the commonly used vaginal estrogen cream, estradiol, for the treatment of GSM. Not only would this be one of the first randomized controlled trials conducted in the US examining this non-hormonal alternative to the standard of care for GSM, but also the vulvovaginal system questionnaire (VSQ), would be the first to be used in a study on this issue.

The studies cited earlier primarily use some combination of the following measurement tools: VAS for vaginal symptoms (dryness, itching, burning, and dyspareunia), physical exam findings, and vaginal maturation index (VMI). Vaginal maturation index is a qualitative measure of hormonal influences on the vaginal epithelium. It measures the percentage of parabasal, intermediate, and squamous cells appearing on a smear and is a valuable tool when comparing the changes in two samples of the same patient (14).

While this study proposes using these aforementioned evaluation tools for GSM, we propose to use the VSQ as the primary outcome to globally assess quality of life as reported by the patient. The VSQ is a 21-question survey developed in 2012 that specifically asks about GSM symptoms, their emotional impact, sexual impact, and life impact. Among 120 post-menopausal women, this questionnaire was found to have reliability and internal consistency (15). Most importantly, in the absence of a gold standard instrument to assess the quality of life impact of GSM, this questionnaire is a critical new tool. It is more nuanced and disease-specific than VAS scoring, and thus far, an underutilized tool to understand the significant psychological impact of this disease. Because GSM is a symptom-driven disease and patients will likely adhere to a treatment plan if they perceive symptomatic improvement, this study’s primary endpoint of treatment success will be measured by improvement in VSQ scoring.

In summary, the goal of this study is to compare and assess the acceptance and effectiveness of the non-hormonal alternative, HLA, to the standard of care, vaginal estrogen, for the treatment of GSM using a randomized, controlled, parallel trial. The primary objective will be assessed by the disease-specific, quality-of-life VSQ score that no study on this investigational product has used thus far. Further, this pilot randomized trial will be the basis for the protocol for assessment of effectiveness in a larger randomized trial.

CONFIDENTIAL

